4.1.6 Safety Monitoring

- The study will be overseen by an SRC composed of the Medical Monitor and 2 voting members from the Sidney Kimmel Comprehensive Cancer Center at Johns Hopkins. The SRC will convene to review data and discuss next steps at the end of every dose level (once all patients complete the 10-week evaluation period), the data have been cleaned, and the DLT outcomes are determined. In addition, the SRC will meet every 6 months at minimum, and as needed to review AEs. The Principal Investigator and study biostatistician will attend SRC meetings. The SRC will sign off on each dose level before activation of a new dose cohort or expansion of a dose cohort may begin.
- All women of childbearing potential (WOCBP) should be instructed to contact the Investigator immediately if they suspect they might be pregnant (eg, missed or late menstrual period) at any time during study participation. The Investigator must immediately notify the Medical Monitor in the event of a confirmed pregnancy in a patient participating in the study.
- The reason(s) for protocol therapy discontinuation, the reason(s) for study removal, and the corresponding dates must be documented in the Case Report Form (CRF).

- Adverse events will be followed for 30 days after the last dose of LC. Patients removed from the study for unacceptable AEs will be followed until resolution or stabilization of the AE.

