4.1.2 Dose Escalation

Following tumor resection, eligible patients who have signed the Informed Consent Form (ICF) will be assigned a dose of LC.

There will be a maximum of 4 dose levels assessed in this study. The first cohort of patients will start at Dose Level 1 (Table 4). If indicated based on the number of observed DLTs at Dose Level 1, patients may be enrolled in Dose Level -1.

Table 4. Liposomal Curcumin, Radiotherapy, and Temozolomide Dose Escalation Schedule

Dose Level	Dose	
	LC	TMZ
Level -1	240 mg/m ²	75 mg/m ² concurrent RT 150-200 mg/m ² Cycles 1-6 adjuvant
Level 1 (Starting Dose)	300 mg/m ²	
Level 2	350 mg/m ²	
Level 3	400 mg/m ²	

LC = liposomal curcumin; RT = radiotherapy; TMZ = temozolomide

The decision whether a new patient should be assigned to the current dose level or to a higher or lower dose level (escalation or de-escalation) is a function of the number of patients already treated at the current dose level, the number of patients who experienced a DLT at the current dose level, and the number of patients who have neither experienced a DLT nor completed their 10-week DLT evaluation period. The Safety Review Committee (SRC) will oversee dose level decisions throughout the dose escalation phase of the study.

All participating sites are expected to notify the Sponsor when a DLT has occurred.

The study will enroll and treat patients in cohorts of 3 in the dose escalation phase. The first cohort will receive 300 mg/m² (Dose Level 1) of LC weekly. The target DLT risk is 30%. During the assessment window, planned doses will be dropped if the data suggest a $\geq 95\%$ probability that the dose will produce a DLT risk $> 30\%$. Using the proposed time-to-event Bayesian optimal interval (TITE-BOIN) design, enrollment in the escalation phase will stop when 12 patients are assigned to the same dose level or when a total of 24 patients have been treated, whichever happens first.

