Once the MTD is determined, an additional 6 patients will be treated in an expansion cohort at this dose level or at a lower dose level determined to be the RP2D. For the expansion cohort, patients will continue to be monitored for occurrence of DLTs. If 2 of the first 5 patients or if ≥ 2 of 6 patients experience a DLT, the Principal Investigator will discuss with all study Investigators and with the Medical Monitor and/or SRC whether further addition of patients is needed to re-assess the MTD. Monitoring of all safety and toxicity data will be done by the Principal Investigator and the SRC on a real-time basis.

In the absence of treatment delays due to AEs, treatment for an individual patient may continue until the completion of standard therapy (until the end of Adjuvant Cycle 6) or until one of the following criteria applies:

- Disease progression

- Intercurrent illness that prevents further administration of treatment
- Unacceptable AEs
- Patient decides to withdraw from the study
- General or specific changes in the patient's condition render the patient unacceptable for further treatment in the judgment of the Investigator
- Clinical progression
- Patient noncompliance
- Pregnancy
- Termination of the study by the Sponsor
- The drug manufacturer can no longer provide the study agent

Toxicities requiring dosing delay or modifications will result in dose adjustments as outlined in [Section 5.10](#) (the minimum dose is 240 mg/m²).

Additional details of the study design and escalation decisions are in [Section 9](#).

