9.1.5 Safety Review Committee

The study will be overseen by an SRC composed of 3 voting members (the Medical Monitor and two additional members). The SRC will convene to review data and discuss next steps at the end of every dose level (once all patients complete the 10-week evaluation period), when the data have been cleaned, and the DLT outcomes are determined. In addition, the SRC will meet every 6 months at minimum, and as needed to review AEs. The Principal Investigator and study biostatistician will attend SRC

meetings. The SRC will sign off on each dose level before activation of a new dose cohort or expansion of a dose cohort may begin.

9.1.6 *Dissemination of Clinical Study Data*

This study will be posted on clinicaltrials.gov. Publication policies are described in [Section 9.1.11](#).

9.1.7 *Data Quality Assurance*

- All patient data relating to the study will be recorded on printed or electronic CRF (eCRF) unless transmitted to the Sponsor or designee electronically (eg, laboratory data). The Investigator is responsible for verifying that data entries are accurate and correct by physically or electronically signing the CRF.
- The Investigator must maintain accurate documentation (source data) that supports the information entered in the CRF.
- The Investigator must permit study-related monitoring, audits, IRB/IEC review, and regulatory agency inspections and provide direct access to source data documents.
- Monitoring details describing strategy (eg, risk-based initiatives in operations and quality such as Risk Management and Mitigation Strategies and Analytical Risk-Based Monitoring), methods, responsibilities and requirements, including handling of noncompliance issues and monitoring techniques (central, remote, or on-site monitoring) are provided in the Monitoring Plan.
- The Sponsor or designee is responsible for the data management of this study including quality checking of the data.
- The Sponsor assumes accountability for actions delegated to other individuals (eg, contract research organizations).
- Study monitors will perform ongoing source data verification to confirm that data entered into the CRF by authorized site personnel are accurate, complete, and verifiable from source documents; that the safety and rights of patients are being protected; and that the study is being conducted in accordance with the currently approved protocol and any other study agreements, ICH GCP, and all applicable regulatory requirements.

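### The Safety Review Committee's full-follow-up condition is not reconciled with the Table 10 rules that change dose while patients are pending

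*Protocol*

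**What the plan says.** **The committee text.** Section 4.1.6 has the SRC convene "at the end of every dose level (once all patients complete the 10-week evaluation period"), once data are cleaned and DLT outcomes are known. It adds: "The SRC will sign off on each dose level before activation of a new dose cohort or expansion of a dose cohort may begin". Its other meetings are described as follows: "In addition, the SRC will meet every 6 months at minimum, and as needed to review AEs". Section 9.1.5 repeats the arrangement, including "once all patients complete the 10-week evaluation period".

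**The dose-finding text.** Section 4.1.2 makes one input to each dose decision "the number of patients who have neither experienced a DLT nor completed their 10-week DLT evaluation period". Section 8.4.8 presents the handling of pending patients as what distinguishes TITE-BOIN from most phase 1 designs. Table 10 in section 8.4.9 carries a column for the number pending and suspends accrual only when more than half of the patients at the dose are pending.

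**Text linking the two.** Section 4.1.2 states: "The Safety Review Committee (SRC) will oversee dose level decisions throughout the dose escalation phase of the study". Section 5.7 says the SRC assigns doses using TITE-BOIN, and section 5.10 has the SRC and the investigator decide increases and decreases in line with it.

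**The concern.** One committee is given two conditions for acting. Its dose-level review waits for every patient to finish 10 weeks. The algorithm it is told to apply exists so that it need not wait.

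The conflict is clearest for a move to a level not yet opened, because the sign-off sentence plainly covers that. It is unclear whether sign-off also covers a return to a level already opened, or a further cohort at the same level; section 5.10 speaks of expanding a cohort to mean adding patients at one level. The end of a dose level is also not defined, although the design can come back to a dose.

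What is at stake is the dose given to the next cohort, in both directions:

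- At 3 evaluable, 0 DLTs, 1 pending, Table 10 escalates. If the pending patient then has a DLT, the row for 3 evaluable, 1 DLT, 0 pending says stay.
- At 3 evaluable, 1 DLT, 1 pending with WSTFT at or below 0.88, Table 10 de-escalates. If that patient finishes without a DLT, the complete-data row says stay.

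Section 8.4.10 mentions no full-follow-up condition, so the reader cannot tell whether Table 11 describes the trial that would be run under the SRC text.

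**Working it through.** **1. Table 10 is a genuine pending-patient rule.** With target φ = 0.30 and the usual BOIN limits 0.6φ and 1.4φ, the boundaries are 0.2365 and 0.3585 (section 8.4.8 states 23.6% and 35.9%). The WSTFT cut-off is c − (nλ − r)(1 − p)/p, where p = (r + 0.15)/(n − c + 1), n is patients at the dose, r is DLTs and c is pending.

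- n = 3, r = 1, c = 1: p = 1.15/3 = 0.383, and 1 − (3 × 0.3585 − 1) × 1.609 = 0.88, as printed.
- n = 6, r = 1, c = 3: p = 1.15/4 = 0.2875, and 3 − (6 × 0.2365 − 1) × 2.478 = 1.96, as printed.

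All 23 cut-offs and the elimination limits (3/3, 4/6, 5/9, 7/12) reproduce.

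**2. Rows affected.** The rows for 12 patients are left out, since "enrollment in the escalation phase will stop when 12 patients are assigned to the same dose level".

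| Patients at dose | Rows | Escalation possible with ≥1 pending | De-escalation possible with ≥1 pending | WSTFT rows | Suspend rows |
|---|---|---|---|---|---|
| 3 | 7 | 1 | 2 | 1 | 2 |
| 6 | 13 | 4 | 5 | 5 | 3 |
| 9 | 18 | 6 | 6 | 8 | 4 |
| Total | 38 | 11 | 13 | 14 | 9 |

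So 11 + 13 = 24 of 38 rows allow a dose change with someone pending. If full follow-up applied to every decision, 14 + 9 = 23 rows could never be used.

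**3. How often it arises.** Section 8.4.10 assumes Poisson accrual of 1 patient per 2 months. Ten weeks is about 2.30 months. Ignoring DLTs, the last patient of a cohort is still in the window at the next arrival with probability 1 − exp(−2.30/2) = 68%.

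**4. Simulation of Table 10 without the SRC condition.** Settings: 6000 trials per scenario; cohorts of 3; stop at 12 on a dose or 24 in total; Weibull times with 65% of DLTs in the second half of the window; start at the second dose column of Table 11. Only moves that open a level for the first time are counted. Scenario 4 is omitted because its true rates are not shown. Each cell gives the result if patients arriving during a Table 10 suspension are lost / if they wait.

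| Scenario | Openings made with a patient pending (%) | Of those, different dose on complete data (%) | Trials with at least one such opening (%) |
|---|---|---|---|
| 1 | 57.5 / 68.1 | 37.5 / 39.5 | 58.9 / 69.2 |
| 2 | 60.5 / 71.7 | 40.3 / 40.1 | 63.4 / 75.2 |
| 3 | 55.2 / 69.6 | 24.2 / 23.2 | 67.5 / 80.2 |
| 5 | 54.5 / 66.5 | 32.7 / 32.9 | 55.2 / 67.6 |

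Monte Carlo standard error is about 0.6 point for the opening shares. A separate coding gave 53–60% / 65–72% for openings with a patient pending, and 23–42% of those differing.

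**5. The first decision** (400,000 draws per rate). True DLT rates at the starting dose are 0.13, 0.30, 0.47 and 0.55 (Scenarios 3, 2, 1 and 5).

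- At 3/0/1, the pending patient goes on to a DLT in about 8, 20, 35 and 43% of cases.
- At 3/1/1, WSTFT is at or below 0.88 in 93–95% of cases. That patient then finishes without a DLT in 91, 78, 64 and 56%.

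With weights 20/30/50 spread evenly within thirds, WSTFT 0.88 = 0.5 + 0.5 × 0.76, or 9.2 of 10 weeks.

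**The case against.** A reading without contradiction is available. Sections 4.1.2, 5.7 and 5.10 place the SRC inside the TITE-BOIN decisions with no 10-week condition. Section 4.1.2 also says "Monitoring of all safety and toxicity data will be done by the Principal Investigator and the SRC on a real-time basis". The sign-off sentence names no follow-up of its own, so the end-of-level review could be an additional look at cleaned data. This is fair as far as it goes, but no passage says so. The real-time sentence concerns safety monitoring and sits in the expansion paragraph, and the as-needed meetings are for AE review. Nothing lifts the 10-week condition from the review at which next steps are discussed.

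The count of 24 rows is wider than the certain conflict. De-escalation from Level 2 or 3 returns to an open level; from the starting dose, only the move to Level -1 opens a lower one. This stands, and it is why the simulation counts first-time openings only.

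The different-dose percentages mostly show how any design that decides with pending patients behaves, which section 8.4.8 adopts openly. This also stands. They are conditional and mix directions: for escalations made with a patient pending the figure is about 11% in Scenario 3, 21–23% in Scenario 2 and 31–45% in Scenarios 1 and 5. Moves down to Level -1 raise the pooled figure in Scenarios 2 and 3. Per first-time opening of any kind it is about 13–29%. The percentages measure how far the two readings diverge; they are not evidence against TITE-BOIN.

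**Conclusion.** The concern holds. The protocol states two conditions for moving to a new dose level and does not say which one SRC sign-off must meet. The case rests on the text, which appears in both SRC sections and so is not a slip in one place. The figures show that the situation would be routine (55–72% of first-time openings, 55–80% of trials) and that the choice of reading can change the next dose.

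The figures depend on the planned accrual, on the first column of Table 11 being Level -1, on even weighting within thirds, and on how arrivals during a suspension are handled. Comparable simulations of the Table 10 rules match the mean sample sizes in Table 11 to within about 2 patients, but their durations run about 2–5 months short. No effect on trial duration is claimed: it depends on whether patients arriving during a closure are lost or wait, which the protocol does not say. No bias in MTD selection is claimed either.

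**What to change.** Reconcile sections 4.1.6 and 9.1.5 with 4.1.2, 8.4.8, 8.4.9 and Table 10 in a single rule. It should state what follow-up SRC sign-off requires at each decision, and whether sign-off applies to every cohort, every dose level, or only the first opening of a level.

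- If the pending-patient rules govern, amend the two SRC sections to say that sign-off uses the DLTs, the number pending and the WSTFT at the decision date. This costs wording only.
- If full follow-up is kept, remove the Table 10 rows that can no longer apply. Re-run Table 11 with that condition and a stated rule for patients who arrive during a closure. This costs a table edit and a simulation re-run.

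Neither route needs extra patients. The choice between them belongs to the sponsor and the SRC.

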4.2 Scientific Rationale for Study Design

Administration of CRT is the standard of care for patients with HGG. In this study, LC will be used in combination with standard therapy.

4.3 Justification for Dose

A recommended starting dose for weekly administration has been established at LC 300 mg/m² IV. The maximum dose in the Phase 1b trial was 300 mg/m² (Greil et al, 2018).

In an FIH safety and PK study in healthy patients, doses ranging from 1 to 400 mg/m² were administered with premedication of diphenhydramine alone.

The systemic safety of LC was good over the dose range between 10 and 320 mg/m². In patients dosed at 400 mg/m², markers of hemolysis were observed, without clinical symptoms.

5 STUDY POPULATION

Prospective approval of protocol deviations to recruitment and enrollment criteria, also known as protocol waivers or exemptions, is not permitted.

5.1 Inclusion Criteria

Women and members of minority groups will be actively recruited. No exclusion to this study will be based on gender, race, or ethnicity.

Patients are eligible to be included in the study only if all of the following criteria apply:

1. Capable of giving signed informed consent as described in [Section 9.1.3](#) (Appendix 1) that includes compliance with the requirements and restrictions listed in the ICF and in this protocol.
2. ≥ 18 years of age
3. Histologically confirmed HGG (WHO grade III or IV, including GBM, astrocytoma, gliosarcoma, *H3K27M* mutant diffuse midline glioma). Patients with methylated or unmethylated O(6)-methylguanine-DNA methyltransferase (MGMT) promoter are eligible, as are IDH WT and mutant patients as long as the treatment plan is for combined RT/TMZ. The neuropathologic diagnosis of HGG will be made at the respective institution. If any question arises regarding the accuracy of the neuropathologic diagnosis, slides (and pathological blocks, if necessary) will be centrally reviewed.
4. Planning standard therapy with TMZ and RT for 6 weeks
5. Karnofsky Performance Scale (KPS) $\geq 60\%$ ([Section 9.6](#) [Appendix 6])
6. Adequate organ and marrow function defined as:

Hgb	> 9 g/dL
ANC	$\geq 1500/\mu\text{L}$
Platelet count	$\geq 100,000/\mu\text{L}$
Total bilirubin	≤ 1.5 * institutional ULN
AST and ALT	≤ 3 * institutional ULN
Creatinine	≤ 1.5 * institutional ULN

OR

Estimated glomerular filtration rate (eGFR)	≥ 60 mL/min/1.73 m ² unless data exist supporting safe use at lower values of renal function, but eGFR must be ≥ 30 mL/min/1.73 m ²
---	---

7. Patients with human immunodeficiency virus (HIV) who are on effective antiretroviral therapy are eligible if the viral load was assessed as undetectable within 6 months prior to baseline.
8. Women: WOCBP must agree to use adequate contraception (hormonal or barrier method of birth control or abstinence) prior to study entry and for the duration of study participation.

Men: must agree to use adequate contraception prior to study entry, for the duration of study participation, and for 4 months after completion of LC administration.

5.2 Exclusion Criteria

Patients are excluded from the study if any of the following criteria apply:

1. Any concurrent cancer diagnosis that is untreated, actively treated, or has undergone any therapy (RT, cytotoxic, targeted, immunotherapeutic, etc) within 2 years of study enrollment, with the exception of squamous or basal cell skin cancer
2. Patient has not recovered from AEs due to prior anticancer therapy (ie, residual toxicities > Grade 1), with the exception of alopecia
3. Receiving any other investigational agent
4. Active infection requiring systemic antibiotics
5. History of allergic reaction to compounds that are chemically or biologically similar to LC (see [Section 5.5.1.2](#) and [Section 5.5.1.3](#))
6. Patient is taking a medication that may potentiate hemolysis
7. Unstable angina or myocardial infarction within the past 6 months
8. Prolonged QTc interval, Bazett formula (QTcB) (> 450 msec for males or > 460 msec for females)
9. Psychiatric illness or social situation that could limit compliance with study requirements
10. Pregnant or breastfeeding

5.3 Screen Failures

Screen failures are defined as patients who consent to participate in the clinical study but do not meet the eligibility criteria. A minimal set of screen failure information is required to ensure transparent reporting of screen failure patients to meet the Consolidated Standards of Reporting Trials (CONSORT) publishing requirements and to respond to queries from regulatory authorities. Minimal information includes demography, screen failure details, eligibility criteria, and any serious adverse event (SAE).

Individuals who do not meet the criteria for participation in this study (screen failure) may be rescreened. A patient who is rescreened is required to sign another ICF.

5.4 Study Intervention

Study intervention is defined as any investigational intervention(s), marketed product(s), placebo, or medical device(s) intended to be administered to a study patient according to the study protocol.

5.5 Study Interventions Administered

Table 5. Regimen Description - Concurrent CRT Period

Agent	Premedications / Precautions	Dose	Route	Schedule	Cycle Length
LC	Dexamethasone 4 mg IV Diphenhydramine 25 mg IV	Per treatment assignment	IV over 3 hr	Weekly: Weeks 1, 2, 3, 4, 5, 6	6 weeks
TMZ	No food 2 hr before and after dosing Antiemetic (eg, ondansetron, prochlorperazine) 30 minutes before dosing Stool softener PRN	75 mg/m ²	PO	Daily during term of RT	
RT		2 Gy	External beam therapy	Monday-Friday	

IV = intravenous; LC = liposomal curcumin; PO = per os (oral); PRN = pro re nata (as needed); RT = radiotherapy; TMZ = temozolomide

Table 6. Regimen Description - Post-CRT Period

Agent	Premedications / Precautions	Dose	Route	Schedule	Cycle Length
LC	Dexamethasone 4 mg IV Diphenhydramine 25 mg IV	Per treatment assignment	IV over 3 hr	Weekly: Weeks 7, 8, 9, 10	4 weeks

IV = intravenous; LC = liposomal curcumin

Table 7. Regimen Description - Adjuvant Period

Agent	Premedications / Precautions	Dose	Route	Schedule	Cycle Length
LC	Dexamethasone 4 mg IV Diphenhydramine 25 mg IV	Per treatment assignment	IV over 3 hr	Weekly: Adjuvant Cycles 1-6: Weeks 1, 2, 3, 4 of each cycle	4 weeks
TMZ	No food 2 hr before and after dosing	150-200 mg/m ² (Cycles 1-6)	PO	Daily	

Agent	Premedications / Precautions	Dose	Route	Schedule	Cycle Length
	Antiemetic (eg, ondansetron, prochlorperazine) 30 minutes before dosing Stool softener prn				

CRT = chemoradiotherapy; IV = intravenous; LC = liposomal curcumin; PO = per os (oral); PRN = pro re nata (as needed); TMZ = temozolomide

5.5.1 Curcumin

Curcumin is a natural product found in the plant turmeric.

5.5.1.1 General Information

Commercial name: LipoCurc

Chemical name: Diferuloylmethane

Molecular formula: C₂₁H₂₀O₆

Molecular weight: 368.38

International Union of Pure and Applied Chemistry (IUPAC) name: (1E,6E)-1,7-bis (4-hydroxy- 3-methoxyphenyl) -1,6- heptadiene-3,5-dione

How supplied: Polymun Scientific GmbH (Vienna, Austria)

5.5.1.2 Potential Toxicity of Liposomal Curcumin

No specifically known drug interactions will exclude patients from enrollment. In early studies, curcumin has been shown to exaggerate effects from *Ginkgo*, hypoglycemic agents, and cholesterol-lowering agents, and patients should be monitored for these metabolic effects or encouraged to reduce or eliminate these medications from their regimen. According to in vitro studies, there is no to minimal inhibition or induction of the common CYP450 drug metabolism enzymes. As part of the enrollment/informed consent process, the patient will be counseled on the risk for interactions with other agents, and what to do if new medications need to be prescribed or if the patient is considering a new over-the-counter medicine or herbal product.

